1.0 Background and Rationale

1.1 Product to be tested

The product to be tested is designed to stimulate the net synthesis of body protein, including muscle protein. The composition is protected by intellectual property and is based on a specially formulated mixture of essential amino acids (EAAs) and whey protein. The overriding metabolic goal of the composition is to maximally stimulate the rate of net muscle protein synthesis. The stimulation of protein synthesis is the metabolic basis for increases in muscular strength and function, and is crucial for increased biogenesis of mitochondria.

1.2 Product composition

The product composition is protected by intellectual property. It contains a combination of ingredients designed to stimulate muscle protein synthesis and to ultimately induce long-term improvements in muscle function and size.

Muscle Protein Synthesis: EAAs are the key to rapid recovery of muscle. EAAs are the “active” components of dietary protein, meaning that they are the amino acids contained in dietary protein that actually stimulate the production of new muscle protein. In fact, EAAs are the only dietary macronutrients that are required for survival. They are “essential” because the body cannot produce them. There are 9 dietary EAAs. There are 11 more dietary non-essential amino acids that are not required in the diet because they can be produced in the body. The composition is based on a blend of 8 of the 9 EAAs. In addition to being the “active” components of dietary protein, EAAs also have the advantage over intact protein because free EAAs are absorbed from the intestine more quickly and more completely than amino acids contained in protein, which require digestion before absorption. Finally, the relative amounts of each EAA can be tailored for any specific metabolic function. In the case of the composition to be tested, the EAA formulation is designed to maximally stimulate muscle protein synthesis in healthy individuals under the age of 50 y.

Intact Protein: Intact proteins are popular dietary supplements to stimulate muscle protein synthesis. While EAAs have a distinct advantage over intact protein in terms of the amount of muscle protein produced following exercise, the response to intact protein is sustained over a longer time than free EAAs because of the slower absorption. The composition combines the

benefits of free EAAs as well as intact protein. The unique combination of EAAs and intact protein cause an immediate increase in muscle protein synthesis (due to the EAAs), and the response is sustained by the slower entry into the body of the EAAs contained in the intact protein.

1.3 Previous research on the topic

The primary goal of the composition is to promote muscle protein synthesis and the balance between synthesis and breakdown. Muscle protein synthesis is most effectively stimulated by EAAs. The response of protein synthesis following EAAs is more than twice as large as a comparable dosage of whey protein (1). Oral ingestion of 2 x 6 g doses of EAAs, taken one hour apart after exercise, induces a greater response of muscle protein turnover than any other nutritional strategy (2). The magnitude of response to EAAs after exercise is dose dependent. The anabolic response to 6 g of EAAs was twice that of the response to 3 g (2,3). Addition of non-essential amino acids to EAAs provides no extra benefit in terms of muscle protein synthesis (4,5).

We assert that the optimal profile of EAAs for young, healthy subjects differs from that for elderly individuals. In contrast to the case for older individuals, there is no requirement for a disproportionate amount of leucine above and beyond to fulfil its requirement as a precursor from protein synthesis. Whereas a disproportionately large dose of dietary leucine relative to the other EAAs amplifies the stimulation of muscle protein synthesis in metabolically-challenged circumstances such as aging (6), a large dose of leucine is not necessary in younger individuals. A large dose of leucine activates mTOR and other factors that are involved at the molecular level in regulating the rate of muscle protein synthesis (7). While this action of leucine is helpful when the activity of mTOR and associated factors are blunted, such as occurs in aging. However, mTOR activity is not rate-limiting in young, healthy individuals. Therefore, a high proportion of leucine in the composition would be redundant in terms of activation of mTOR. By reducing the proportion of leucine in the composition, the profile of the EAAs in the composition more closely reflects the profile of EAAs in muscle protein. This is advantageous since the limiting step in muscle protein synthesis in healthy young individuals is the availability of EAA precursors in proportion to the profile of EAAs in muscle protein (8).

The profile of EAAs of the composition is specifically designed for maximal stimulation of muscle protein synthesis following exercise.

The use of free EAAs is advantageous in terms of being able to determine the exact profile of the amino acids. Also, unlike intact protein, EAAs are rapidly and extensively absorbed (9).

The rapid peak response in plasma EAAs is a key reason for their effectiveness (10). On the other hand, the total duration of the response is limited, because just as the concentrations of EAAs in the blood rise rapidly, they fall rapidly as well (2). For this reason, the composition contains protein in addition to the EAAs to prolong the anabolic response in the recovery period.

EAAs are the “active” components of dietary protein that are primarily responsible for the stimulation of protein synthesis. Non-essential amino acids (NEAAs) are not required in the short term. This is because the NEAAs are normally produced in the body at fast enough rates to avoid deficiencies. On the other hand, studies performed in livestock suggest that maximal long-term animal growth and development is achieved with a balance of about 20-30% NEAAs and 70- 80%EAAs (11). The addition of a small amount of intact protein to a mixture of EAAs is the most efficient way to incorporate the appropriate amount of NEAAs into a dietary supplement designed to stimulate muscle protein synthesis over the long-term. A number of studies have determined that whey protein is the most effective intact dietary protein in terms of stimulation of muscle protein synthesis after exercise (12,13). Whey protein is approximately 50% EAAs and 50% NEAAs. By combining a small amount of whey protein with EAAs, the necessary intake of NEAAs is provided in a format (I,e., intact protein) that, while not as effective as the EAA mixture, nonetheless has its own stimulatory effect on muscle protein synthesis. The combination of free EAAs and intact protein give an immediate response (from the free EAAs) which is prolonged over time by the slower digestion of the intact protein.

The idea of combining a specific formulation of EAAs with an intact protein to obtain both an immediate as well as a more sustained response of protein synthesis is novel. Previous studies have added leucine to whey protein, but the inventor’s laboratory found this approach to not be effective (14). If only leucine is added to intact protein, an imbalance in the availability of the other EAAs is created that limits precursor availability for protein synthesis. The same limitation is true in the case of providing only branched chain amino acids. A unique aspect of

the composition to be investigated is that a balanced mixture of all the EAAs is added to the whey protein source. With this approach, the rapid response of muscle protein synthesis to the free EAAs is sustained by the more gradual absorption of the EAAs from the whey protein. The unique combination of whey protein and a specially formulated EAA mixture that coincides with the proportionate demand for precursors for stimulated muscle protein synthesis provides a rapid and sustained response.

The stimulation of both the number and function of the mitochondria is central to improved functional capacity of muscle. The EAA leucine in the composition acts as a nutraceutical to stimulate mitochondria biogenesis (15), and the free amino acids and protein stimulate the synthesis of new mitochondrial proteins (16). Therefore, the combination of free EAAs increases the ability of the muscle mitochondria to produce energy.

2.0 Hypothesis

We propose that consumption of the EAA/protein composition will stimulate the net gain (net protein synthesis) of body protein in a dose-dependent manner. We further propose that the magnitude of increase in net protein synthesis will be greater than induced by the consumption of the same amount of whey protein isolate, which is currently the most popular supplement on the market targeting the stimulation of muscle protein synthesis.

3.0 Study Design and Procedures

We will study a total of up to 20 healthy male and females between 18 and 50 years of age. We will use a randomized, two-period, stable isotope (Cambridge Isotope Labs, Tewksbury, Mass.) infusion study: 4.5-hour basal fasted period and 4-hour post-meal period (total 8.5-h time period). The principal end-point will be the total anabolic response (whole body protein synthesis minus breakdown) and the secondary end point will be muscle protein fractional synthetic rate (FSR) over the 4 hours following the consumption of either the test composition or whey protein. The plasma amino acid response will also be a secondary end point.

We will utilize two distinct arms within this protocol. Arm 1 will consist of a group of subjects who will perform a randomized, single blind cross-over (two stable isotope studies) between the two doses of the EAA/protein study supplement, with a \geq oneweek washout period between stable isotope studies. Arm 2 will consist of a group of subjects (with similar gender composition) who will undergo one stable isotope study during which they will ingest the whey protein isolate study supplement. Subjects will be enrolled into the double stable isotope study arm, utilizing the specific consent form. After Arm 1 enrollment is completed, unique future subjects will be enrolled into Arm 2 – the single stable isotope arm, using the specific consent form.

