3.1 Study Visits

Visit 1: subjects will come to the UAMS IOA 3rd floor for informed consent discussion. Once consent is obtained, subsequent study procedures will be performed. A medical history including allergies and list of current medications will be obtained (printed from Epic if they are a UAMS patient). Subject height and weight will be measured. A blood sample will be drawn for complete blood count [CBC]. Females of child bearing capacity will be asked to provide a urine sample for pregnancy testing. Blood and urine samples will be sent to LabCorp for the screening tests. A physical exam and vital signs will be performed at this visit or at visit 2. A DEXA scan for whole-body analysis will be performed in the PI's lab at UAMS (or at visit 2). Subjects can get a copy of their CBC and DEXA scan upon request. Any abnormal findings will be discussed with them by the study nurse and/or physician. Based upon the results of the screening blood sample, visit 2 will be scheduled.

Visit 2: Subjects return to the UAMS IOA having fasted overnight from 10:00 P.M. They will be asked about any adverse events since last visit. If not performed at visit 1, the physical exam and/or DEXA scan will be performed at this visit. For subjects who enrolled into the double infusion arm, randomization will be performed as to the order of supplement dose ingestion. After vital signs are measured, the study nurse will insert an IV catheter into a vein on each of the subjects' arms. One catheter is used to infuse the stable isotopes L-ring-D5 phenylalanine and 2H₂-tyrosine. The other is to allow for periodic blood sampling, warming the arm by means

of a heating pad or a heated plastic box. After an initial blood sample is obtained, the study nurse will infuse the priming doses of the two above isotopes as well as a priming dose of 2H4-tyrosine. Constant infusion of isotopes commences immediately after the priming doses are completed. A timer will be started, and blood/muscle samples will be obtained according to the schedule below. The appropriate study supplement will be served directly after the second muscle biopsy procedure. Subjects will be asked to consume their supplement within 2 minutes.

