3.4 Randomization for EAA/protein Arm

Study staff will strive to maintain gender balance between the two arms. A randomization list will be implemented to reveal which dosage of EAA/protein will be tested first in the case of the cross-over study (Arm 1).

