3.6 Sample Storage

Blood and muscle samples will be kept frozen at -80 degrees Centigrade or colder once the initial processing has taken place. Samples shall be stored in appropriate freezers in the PI's laboratory, located in a restricted area inside the UAMS IOA building. Said freezers are monitored continuously for proper temperature and working condition. With explicit permission via the ICF, all biological samples will be kept indefinitely for future IRB-approved uses. All blood and muscle samples shall be identified using a unique study acronym. None of a subject's personal identifiers shall be present on any biological sample.

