7.0 Data Analysis

7.1 Statistical Analysis plan

The purpose of this study is to estimate and compare the effect of two different nutritional beverages on total anabolic response (TAR) and muscle protein synthesis (MPS). To this end, an analysis of covariance (ANCOVA) model will be employed to compare the protein sources with respect to mean response (either TAR or MPS) after adjusting for basal measures. If a significant protein group effect is detected, then pairwise comparisons will be performed to determine if the two sources or two doses differ. In this case, the Tukey-Kramer method will be used to adjust for multiple comparisons. A 5% will be used to determine statistical significance.

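### The comparison of EAA/protein with whey is not randomised: whey subjects are enrolled only after the EAA/protein arm is full, so protein source cannot be separated from enrolment period

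*Combined protocol and SAP*

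**What the plan says.** Section 3.0 introduces the whole study with the words "We will use a randomized, two-period, stable isotope" infusion study. It then describes two arms. Arm 1 crosses over between two doses of the EAA/protein product. Arm 2 takes whey once. On entry to the arms it says: "After Arm 1 enrollment is completed, unique future subjects will be enrolled into Arm 2". Each arm has its own consent form.

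Randomisation is described only inside Arm 1. Section 3.1 says that for the double-infusion arm "randomization will be performed as to the order of supplement dose ingestion". Section 3.4, whose heading names only the EAA/protein arm, says: "A randomization list will be implemented to reveal which dosage of EAA/protein will be tested first". Between the arms, the only balancing measure is effort on sex: "Study staff will strive to maintain gender balance between the two arms".

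The contrast between arms matters to the trial's claims. Section 2.0 proposes that the increase in net protein synthesis "will be greater than induced by the consumption of the same amount of whey protein isolate". Section 7.1 specifies an ANCOVA that "will be employed to compare the protein sources with respect to mean response (either TAR or MPS) after adjusting for basal measures".

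**The concern.** A subject's product is decided by the date of enrolment, not by chance. Anything that differs between early and late enrollees, such as season, recruitment source, staff practice or tracer lot, falls on one side of the comparison.

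The arms may also attract different volunteers, because people consent to a known schedule. Arm 1 means two infusion days, six biopsies and up to $625. Arm 2 means one day, three biopsies and up to $325.

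Superiority to whey is one of only two hypotheses. If the arms differ in fed-state response for any of these reasons, a significant result cannot be attributed to the product. The unqualified description of the study as randomised would lead readers to assume that it can.

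**Working it through.** **1. What is randomised.** The relevant statements, side by side:

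| Section | What it randomises |
|---|---|
| 3.0 (Arm 1) | the cross-over between two doses |
| 3.1 (visit 2) | dose order, double-infusion arm only |
| 3.2 (visit 3) | order of the beverages, EAA/protein arm only |
| 3.4 | which dose comes first, Arm 1 only |

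No section assigns subjects to EAA/protein or whey at random.

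**2. Aliasing.** Take 24 rows: 8 Arm 1 subjects at two doses and 8 whey subjects. Give the design matrix columns for intercept, dose, whey and late enrolment period. The whey and period columns are identical, so the matrix has rank 3 with 4 columns. No model fitted to these data can estimate the two effects separately.

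**3. Burden and pay.** Section 3.1 schedules muscle samples at 150, 270 and 510 minutes, which is 3 per infusion day: 2 × 3 = 6 in Arm 1 and 3 in Arm 2. From section 3.3, 25 + 300 + 300 = $625 and 25 + 300 = $325.

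**4. The plan's own figure.** For a one-way ANCOVA with k groups and one covariate, λ = N f² / (1 − R²), with k − 1 and N − k − 1 degrees of freedom. Take k = 3, f = 0.484, R² = 0.50 and α = 0.05 (section 7.2).

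- N = 24: λ = 24 × 0.484² / 0.5 = 11.24, df 2 and 20, power 80.0%. This matches Table 1.
- N = 16: λ = 7.50, df 2 and 12, power 56.9%.

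The power statement therefore corresponds to three groups of 8 treated as independent. That layout is used below.

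**5. Size of the exposure.** The documents give no figure for an arm difference, so the shifts are assumptions. Model: y = √0.5·x + e, where x is the basal value, the total SD is 1 and the residual SD is √0.5 = 0.707. There is no product effect. The shift is added to both EAA/protein groups. The test is the planned one: a three-group F test (critical value 3.493), then, only if that is significant, Tukey-Kramer on adjusted means (q critical 3.578). Each setting used 200,000 simulated trials.

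| Shift left after basal adjustment (residual SD) | One given dose v whey | Either dose v whey |
|---|---|---|
| 0 | 1.9% | 3.4% |
| 0.25 | 3.1% | 5.4% |
| 0.5 | 7.5% | 12.3% |
| 0.75 | 16.3% | 25.0% |
| 1.0 | 29.9% | 42.7% |

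The false-positive rate for dose versus dose stays at 1.8 to 2.0% throughout.

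With a within-subject correlation of 0.5 in Arm 1, shifts of 0, 0.5 and 0.75 give 2.0%, 8.0% and 17.2% for one dose, and 3.3%, 11.7% and 23.5% for either dose.

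**6. Favourable case.** In raw units the 0.5 and 0.75 shifts are 0.5 × 0.707 = 0.354 SD and 0.75 × 0.707 = 0.530 SD. Suppose the same raw shift moves basal and fed values equally. With a slope of 0.707, adjustment leaves 0.354 × (1 − 0.707) = 0.10 SD or 0.530 × (1 − 0.707) = 0.16 SD. The rates are then 2.3% and 2.7% for one dose, and 4.0% and 4.8% for either dose.

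**The case against.** The strongest reply is that the design is disclosed and well protected. Sections 3.0 and 3.4 attach randomisation to Arm 1, and a careful reader would not conclude that subjects are randomised to whey. Eligibility, site and infusion schedule are common to both arms. Every infusion has its own same-day basal period, which is the covariate. Pay per infusion visit is the same, up to $300; the totals differ only because Arm 1 has one more visit. Arm 2 opens when Arm 1 *enrolment* is complete, so late Arm 1 infusions may overlap early Arm 2 infusions in calendar time.

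The size is also open to challenge. No document supports a shift of 0.5 SD. The hypothesis concerns equal amounts, so the one-dose column is the relevant one. The hypothesis is also directional, while the sign of any shift is unknown. A shift of +0.5 residual SD gives false superiority in about 7.3% of trials and −0.5 in about 0.07%. If both signs are equally likely, the average is (7.3 + 0.07) / 2 ≈ 3.7%, or about 8% at 0.75 SD, against 0.9% with no shift.

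Finally, subjects randomised to six biopsies might withdraw more often than those randomised to three, which would bring selection back.

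Much of this stands, and it limits the size. It does not answer the point itself. Disclosing the sequence does not make the contrast randomised. Calendar overlap weakens drift in measurement but not selection of who enrols. Basal adjustment works only for differences that show in basal values. Section 3.5's remark that subjects cannot consciously control protein synthesis concerns blinding, not who enters which arm.

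**Conclusion.** The concern holds. The EAA/protein-versus-whey contrast is non-randomised and completely aliased with enrolment period, and the documents never say that this comparison is not randomised. As designed, the second hypothesis cannot be answered causally: a significant difference could reflect the product, the period or the volunteers.

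How much this matters in practice depends on a quantity the documents do not give. For one dose against whey, the false-positive rate rises from 1.9% to about 7.5% or 16% if 0.5 or 0.75 residual SD remains after basal adjustment. It stays below 3% if the same raw shift moves basal and fed values equally. The exposure is therefore mainly to arm differences specific to the fed-state response. The randomised dose comparison within Arm 1 is unaffected.

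Assay batch need not follow arm, since section 3.6 says "Blood and muscle samples will be kept frozen at -80 degrees Centigrade or colder", but the plan does not commit to assaying both arms together. The point should be fixed; it does not stop the trial.

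**What to change.** **Preferred.** Enrol both arms concurrently. Use one consent form that describes both schedules. After consent, randomise subjects 1:1 to Arm 1 or Arm 2 from a single list stratified by sex, and keep the existing list for dose order within Arm 1. Report withdrawals by arm, because the burden differs. Relative to the 8 + 8 in section 7.2, this plans no extra subjects, visits or biopsies.

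The cost is a protocol and consent amendment. Recruitment may also be slower, because every volunteer must accept the possibility of two infusions and six biopsies. The documents give no recruitment rate, so the delay cannot be sized. Withdrawals could require replacements; section 3.0 allows up to 20 subjects, which is 20 − 16 = 4 above the planned number.

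**If sequential enrolment is kept.** In section 3.0, limit the word 'randomized' to the Arm 1 dose order. In section 7.1, state that EAA/protein versus whey is a non-randomised comparison, and report it that way with enrolment dates by arm. Commit to assaying stored samples from both arms together. This costs almost nothing. It does not remove the bias, but it limits the claim to what the design can support.

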3.1 Study Visits

Visit 1: subjects will come to the UAMS IOA 3rd floor for informed consent discussion. Once consent is obtained, subsequent study procedures will be performed. A medical history including allergies and list of current medications will be obtained (printed from Epic if they are a UAMS patient). Subject height and weight will be measured. A blood sample will be drawn for complete blood count [CBC]. Females of child bearing capacity will be asked to provide a urine sample for pregnancy testing. Blood and urine samples will be sent to LabCorp for the screening tests. A physical exam and vital signs will be performed at this visit or at visit 2. A DEXA scan for whole-body analysis will be performed in the PI's lab at UAMS (or at visit 2). Subjects can get a copy of their CBC and DEXA scan upon request. Any abnormal findings will be discussed with them by the study nurse and/or physician. Based upon the results of the screening blood sample, visit 2 will be scheduled.

Visit 2: Subjects return to the UAMS IOA having fasted overnight from 10:00 P.M. They will be asked about any adverse events since last visit. If not performed at visit 1, the physical exam and/or DEXA scan will be performed at this visit. For subjects who enrolled into the double infusion arm, randomization will be performed as to the order of supplement dose ingestion. After vital signs are measured, the study nurse will insert an IV catheter into a vein on each of the subjects' arms. One catheter is used to infuse the stable isotopes L-ring-D5 phenylalanine and 2H₂-tyrosine. The other is to allow for periodic blood sampling, warming the arm by means

of a heating pad or a heated plastic box. After an initial blood sample is obtained, the study nurse will infuse the priming doses of the two above isotopes as well as a priming dose of 2H4-tyrosine. Constant infusion of isotopes commences immediately after the priming doses are completed. A timer will be started, and blood/muscle samples will be obtained according to the schedule below. The appropriate study supplement will be served directly after the second muscle biopsy procedure. Subjects will be asked to consume their supplement within 2 minutes.

At the conclusion of the 8.5-hour infusion study, the IV catheters will be removed and the sites dressed with a sterile bandage. Written and verbal instructions regarding the care of the muscle biopsy site will be provided. A snack and beverage will be offered to subjects. Vital signs will be measured, and subjects will then be free to leave. A follow-up phone call will be made within 72 hours after subjects have left the facility to assess for adverse events related to the stable isotope study visit.

Elapsed time (min., approximate)	Procedure
-0	Blood sample (~6mL)
120	Blood sample (~6mL)
150	Blood sample (~6mL), muscle sample (subject's choice of left or right vastus lateralis ~150mg)
180	Blood sample (~6mL)
210	Blood sample (~6mL)
240	Blood sample (~6mL)
270	Blood sample (~6mL), muscle sample (~150mg), ingest study supplement
290	Blood sample (~6mL)
310	Blood sample (~6mL)
330	Blood sample (~6mL)
360	Blood sample (~6mL)
390	Blood sample (~6mL)

420	Blood sample (~6mL)
450	Blood sample (~6mL)
480	Blood sample (~6mL)
510	Blood sample (~6mL), muscle sample (~150mg)

